## Protocol Synopsis

Protocol	CTP-0005, Version 2.0 IDE # G110022
Study Title	Air X Panders A eroForm Tissue Exp a N Der System for Breast Reconstruction ( XPAND II )
Sponsor	AirXpanders Inc.
Investigational Device	AeroForm® Tissue Expander System v2.5
Intended Use	The AeroForm Tissue Expander System is intended for use in post-mastectomy patients to develop tissue coverage prior to the placement of permanent breast implants. The device is intended for temporary subcutaneous or submuscular implantation and is not intended for use beyond six months.
Study Design	This is a prospective, multi-center, single arm, open-label, continued access clinical study. Subjects who meet the inclusion criteria and agree to participate in the study will be enrolled and implanted with the investigational AeroForm Tissue Expander. If the subject is having a bilateral procedure, the AeroForm expander will be implanted in each side. Subjects will be followed until the first post-operative visit after explant of the tissue expander(s) and exchange for permanent implant(s).
Study Objective	The objective of this study is to allow existing investigators continued access to the AeroForm Tissue Expander to treat patients while the company completes the marketing application and during the review process by FDA.
Primary Outcome Measure	The performance of the device will be evaluated by: Successful tissue expansion with exchange to a permanent breast implant unless exchange is precluded by a non-device related event. The primary endpoint will be analyzed per breast. Breasts in which the expander is removed and/or replaced due to a device related adverse event or a device malfunction will be counted as failures.
Secondary Outcome Measures	The safety of the device will be evaluated by: 
 
• Device related adverse events
 
• All adverse events, regardless of whether serious or there is a causal relationship to the device.
 
• Serious device related adverse events
 
• All serious adverse events, regardless of whether there is a causal relationship to the device.
 
• Device malfunctions leading to expander removal and/or replacement
 

Additional Outcome Measures	The usability of the device will be evaluated by: 
 
• The average number of days to achieve the desired expansion (onset of active expansion to completion of expansion)
 
• The average number of days for completion of stage 1 reconstruction (expander implant to permanent implant).
 
• Subject reported pain ratings at the onset of active expansion and one week after beginning active expansion
 

Protocol	CTP-0005, Version 2.0 IDE # G110022
Study Title	Air XP anders A eroForm Tissue Expa ND er System for Breast Reconstruction ( XPAND II )
	
 
• Overall subject satisfaction
 
• Overall physician satisfaction
 
• Reported device issues
 

Study Population	Women who are planning to undergo immediate or delayed breast reconstruction (unilateral or bilateral) post mastectomy and require tissue expansion to develop sufficient tissue coverage for placement of permanent implant(s). Up to 60 subjects will be enrolled in the study.
Investigational Sites	Up to 7 existing clinical sites will participate in the study. Investigators will be qualified board certified plastic and reconstructive surgeons with experience in breast reconstruction using tissue expanders and prior experience using the AeroForm Tissue Expander System.
Recruitment/Enrollment	Subjects will be recruited from current patient referrals at each site at the same rate of enrollment observed in the pivotal trial (XPAND). Investigators may enroll up to 4 subjects per month. The option of participating in the study will be discussed with the patients at their initial consultation visit and they will be given the informed consent. Once the patient has had adequate time to read the informed consent and have all of their questions answered, they will be asked if they would like to participate in the study. Once an informed consent is signed, patients will be enrolled in the study and scheduled for surgery.
Statistical Analysis Plan	This study is a continued access study and the results of this study will be analyzed in accordance with the statistical analysis plan for the XPAND study (CTP-0003).
Study Duration	Approximately one year
Subject Study Duration	Expected subject participation will be up to 6 months. Subjects will be followed from the time of implant to the first post-operative visit after explant of the tissue expander(s)
Inclusion Criteria	
 
1. Subject is female between the ages of 18-70
 
2. Subject requires tissue expansion as part of breast reconstruction
 
3. Subject is able to provide written informed consent
 
4. Subject is able and willing to comply with all of the study requirements
 
5. Subject has the physical, perceptual and cognitive capacity to understand and manage the at home dosing regimen
 

Exclusion Criteria	
 
1. Subject's tissue integrity is unsuitable for tissue expansion
 
2. Subject has residual gross malignancy at the intended expansion site
 
3. Subject has current or prior infection at the intended expansion site
 
4. Subject has a history of failed tissue expansion or breast reconstruction
 
5. Subject has any co-morbid condition determined by the Investigator to place the subject at an increased risk of complications (e.g., severe collagen vascular disease, poorly managed diabetes)
 
6. Subject is taking any concomitant medications determined by the Investigator to place the subject at an increased risk of complications (e.g., Prednisone, Coumadin).
 

Protocol	CTP-0005, Version 2.0 IDE # G110022
Study Title	Air XP anders A eroForm Tissue Expa ND er System for Breast Reconstruction (XPAND II)
	
 
7. Subject is participating in a concurrent investigational drug or device study.
 
8. Subject is current tobacco smoker.
 
9. Subject is obese (BMI > 33).
 
10. Subject is unwilling to comply with instructions to notify the investigator and discontinue dosing prior to air travel, travel to a higher altitude and during the travel period.
 
11. Subject has an implanted electronic device such as a pacemaker, defibrillator, neurostimulator, or drug infusion device.
 
12. Subject is pregnant or planning on becoming pregnant during the study period.
 
13. Subject has a history of psychological condition, drug or alcohol misuse which may interfere with their ability to use the device safely.
 

# 1 Introduction

## 1.1 Background/Purpose

According to the American Society of Plastic Surgery statistics, 95,589 women underwent breast reconstruction in the United States in 2013. The majority of women chose implant based reconstruction (76,278), with most performed as a two stage procedure using tissue expanders followed by permanent implants (68,607). The current standard of care tissue expanders are filled with saline via needle injection on a periodic basis until expansion is complete. Many women undergoing tissue expansion for breast reconstruction find this process uncomfortable and arduous requiring multiple office visits to complete the filling procedure. Physicians have long sought an alternative to the sterile procedure required to fill the current expanders.

AirXpanders, Inc., located in Palo Alto, CA, has developed a novel remote-control breast tissue expander (AeroForm Tissue Expander System) which is filled from an internal source with carbon dioxide (CO2) eliminating the need for needle injections to fill the expander. This expander has the potential to make the process easier, faster and more comfortable while providing women with some degree of control over the expansion. The system is comprised of an implantable tissue expander which contains a reservoir filled with compressed carbon dioxide (CO2), and an external hand held remote control. The controller activates the opening of an internal valve housed within the CO2 reservoir to release carbon dioxide into the expander.

Enrollment in a prospective, multicenter, randomized, controlled clinical trial to evaluate the safety and effectiveness of the AeroForm tissue expander was completed in the U.S. in 2015. In this study, 150 women were randomized to either the investigational expander or saline expander control group using a 2:1 randomization design. Following mastectomy, subjects underwent a two stage procedure involving the placement of a tissue expander under the pectoralis major muscle and remaining skin of the absent breast. The expanders were placed either at the same time as the mastectomy (immediate reconstruction) or at some point after the mastectomy (delayed reconstruction) in unilateral or bilateral procedures.

Once adequate wound healing was confirmed, the expanders were gradually inflated using the remote control in the investigational group, and by periodic injections of saline in the control group. Once the overlying skin and muscle was stretched enough to provide adequate coverage, the expanders were removed and replaced by permanent breast implants.

This study is a continued access study designed for experienced investigators for the purpose of retaining their skills and experience with the device while the company completes a marketing application and during FDA review. The study is a single arm design with all subjects treated with AeroForm expanders.

## 1.2 Literature Review

The formal concept of surgical tissue expansion was first reported by Neumann in 1957, and further refined for breast reconstruction by Radovan and Argenta in the 1980s. Current standard of care using saline expanders requires months of weekly office visits for bolus injections and is associated with discomfort from high volume inflations, risk of infection and iatrogenic punctures of the expanders

A system designed for gradual, continuous expansion was shown by Bergé and others to be more rapid and well tolerated reducing the time burden and patient discomfort. In the Bergé study, investigators used an osmotic expander that continuously absorbed surrounding tissue fluid after deployment. However, a remaining concern was the inability to control osmotic expanders after they are deployed in the body.

Widgerow tested an expansion device using an external pump connected through tubing to the implanted expander which was controlled by the patient. He showed rapid time courses and patient satisfaction. However, the connector tubing imparted a cumbersome setup for the patient and the fear that prolonged connection to the external environment carries a high risk of contamination. Because the expanded pocket eventually receives a permanent implant, any level of contamination is unacceptable.

Reported complications from tissue expansion are typically due to poor tissue perfusion due to the poor vascularity of thin tissue flaps remaining following the

removal of breast tissue. The major complications involve wound healing issues with tissue necrosis, flap failure and infections which can lead to expander removal and failed reconstruction. Retrospective studies report an overall failure rate of 1.8 to 18%. Complications are exacerbated in this population in patients who undergo neo-adjuvant or adjuvant chemotherapy and radiation treatments for breast cancer.

Published reports published on the use of the AeroForm Tissue Expander System indicate that tissue expansion and breast reconstruction can be accomplished faster using this device with a similar complication rate to that reported in the literature (Connell, Ascherman, Zeidler). Connell and Zeidler also reported that radiation therapy can be delivered successfully with the expander in situ.

### **1.3 Pre-Clinical Testing**

#### **1.3.1 Bench Testing**

The AeroForm Tissue Expander System has undergone thorough verification and validation testing that included:

- Biocompatibility
- Performance and functionality
- Stress and wear
- Sterilization validation
- Transit
- Shelf-life
- Electrical safety
- EMC
- Software validation

#### **1.3.2 Animal Testing**

A pre-clinical study was conducted in February 2009 using two sheep to confirm that the AeroForm Tissue Expander System operated as designed. Results of the *in vivo* sheep model study demonstrated that the device performed as intended (Jacobs). All implants consistently responded to user input via the hand-held remote control, desired volume expansion was achieved and no clinical safety-related issues were identified.

#### **1.4 Human Clinical Testing (PACE I/II, XPAND, ASPIRE)**

The first human feasibility study (PACE 1, Connell) was conducted at one investigational site in Perth, Australia beginning in June 2009. The study was a prospective, open-label, single arm feasibility study and established the safety of the AeroForm System for gradual, incremental breast tissue expansion prior to permanent breast reconstruction, paving the way for further clinical investigations.

Seven subjects were enrolled in the study and 10 AeroForm expanders (Clinical Version 1.0) were implanted in combination with a latissimus dorsi flap procedure. All seven subjects were successful using the device to complete their expansion at home and completed their reconstructions. The average length of active patient dosing was 15 days with a range of 5-22 days. The average time from expander implant to exchange for a permanent implant was 105 days with a range of 69-196 days. During the course of this study, some expanders had a higher than expected degree of permeation and required additional interim dosing. This permeation was traced to a design issue (molding seam) that was eliminated in Clinical Version 2.0.

Beginning in 2011, an additional 33 subjects were enrolled at the same site in the next phase of the study (PACE II, Connell). Sixty-one (61) AeroForm Tissue Expanders (Clinical Version 2.0) were implanted, and all 33 subjects successfully completed expansion and reconstruction. The average time to complete the expansion was 17 days and the average time to complete reconstruction was 90 days.

In a continued access study (ASPIRE) in Australia conducted in 2013 an additional 21 subjects were enrolled with 34 expanders implanted. The average time to complete the expansion was 22 days and the average time to complete reconstruction was 96 days. Two subjects in this study had prolonged courses due to complications related to poor tissue perfusion of dermal flaps that were used as an alternative to the investigators typical latissimus flap procedure.

In parallel to PACE II and ASPIRE, a prospective, multi-center, randomized, controlled clinical trial was initiated in the United States in October 2011 with enrollment completed in December 2014. A total of 150 subjects were treated after randomization (2:1 AeroForm to saline expander - 98 AeroForm, 52 Saline) at 17 sites with 168 AeroForm expanders and 89 saline expanders implanted. The

bilateral rate was 71%. The study was conducted with Clinical Version 2.0 (90 expanders) and Clinical Version 2.5 (78 expanders). Clinical version 2.5 was introduced during the trial to improve the barrier layer of the expander which contains the CO2 and to allow the physicians increased access to the available CO2 in the reservoir.

## 1.5 Marketing Authorizations

The AeroForm Tissue Expander has received CE marketing, but marketing and sales in Europe has not commenced. Additionally, a license approval has been granted by the TGA (Australia), and a limited market release of the product began in September, 2014. Limited data are available from the commercial experiences in Australia.

## 2 Study Rationale

The creation of a stable formed pocket for placement of a permanent implant is the foundation of successful implant based breast reconstruction, which can significantly improve the quality of life for a woman following the devastating effects of breast cancer.

The AeroForm System provides a needle free alternative to standard saline expanders and allows patients to participate in the expansion process with oversight by their physician. Tissue expansion with the AeroForm System eliminates the need for periodic bolus injections and may be performed at the patient's convenience at home under the direction of the physician. The incremental release of CO2 on a daily basis allows a more gradual method of tissue expansion than with saline expanders.

Results of the previous clinical studies provides evidence that the AeroForm expander can be used safely and effectively to create the space needed to support permanent breast implants. Continued access to this technology is necessary to confirm the performance, collect additional usability data and refine best practices for its use.

## 3 Study Design

This is a prospective, multi-center, single arm, open-label, continued access study. Subjects who meet the inclusion criteria and agree to participate in the study will be

enrolled and implanted with the AeroForm Tissue Expander. If the subject is having a bilateral procedure, the investigational expander will be implanted in each side. Subjects will be followed until the first post-operative visit after explant of the tissue expander(s) and exchange to permanent implant(s). The study will be conducted according to IDE regulations.

## **4 Study Objectives**

The objective of this study is to allow existing investigators continued access to the AeroForm Tissue Expander to treat patients while the company completes the marketing application and during the review process by FDA.

### **4.1 Primary Outcome Measure**

The performance of the device will be evaluated by:

Successful tissue expansion with exchange to a permanent breast implant unless exchange is precluded by a non-device related event. The primary endpoint will be analyzed per breast. Breasts in which the expander is removed and/or replaced due to a device related adverse event or a device malfunction will be counted as failures.

### **4.2 Secondary Outcome Measures**

The safety of the device will be evaluated by:

- Device related adverse events
- All adverse events, regardless of whether serious or there is a causal relationship to the device.
- Serious device related adverse events
- All serious adverse events, regardless of whether there is a causal relationship to the device.
- Device malfunctions leading to expander removal and/or replacement.

### **4.3 Additional Outcome Measures**

The usability of the device will be evaluated by:

- The average number of days to achieve the desired expansion (onset of active expansion to completion of expansion)
- The average number of days for completion of stage 1 reconstruction (expander implant to permanent implant exchange).
- Subject reported pain ratings at the onset of expansion and one week after beginning active expansion
- Overall subject satisfaction
- Overall physician satisfaction
- Reported device issues

## **5 Statistical Considerations and Analysis Plan**

### **5.1 Introduction**

This is a prospective, multi-center, single arm, controlled, open-label continued access study. The results will be analyzed in accordance with the statistical analysis plan for the XPAND study (CTP-0003, v 9.0).

All subjects will be followed on an intent-to-treat basis. The primary risk benefit analysis for the device will be assessed based on a per protocol analysis of the primary performance and safety endpoints. Modified Intent-to-Treat and Safety analyses, along with other secondary analyses, will also be completed and reported.

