## **6 Study Population**

The study population will consist of women who are planning to undergo immediate or delayed breast reconstruction (unilateral or bilateral) post mastectomy and require tissue expansion to develop sufficient tissue coverage for placement of the permanent implant(s). Up to 60 subjects will be enrolled in the study.

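### Does deferring the analysis of a single-arm study to the SAP of a randomised trial leave the per-breast primary analysis undefined?

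*Combined protocol and SAP*

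**What the plan says.** Section 5 of the protocol consists of Section 5.1 alone. It describes a "single arm, controlled, open-label continued access study" and states: "The results will be analyzed in accordance with the statistical analysis plan for the XPAND study (CTP-0003, v 9.0"). The synopsis repeats the deferral without a version number. Section 5.1 adds that subjects are followed by intention to treat, that the main risk-benefit assessment rests on "a per protocol analysis of the primary performance and safety endpoints", and that modified intention-to-treat and safety analyses will also be reported.

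The borrowed plan belongs to a trial in which "150 women were randomized to either the investigational expander or saline expander control group using a 2:1 randomization design" (Section 1.1). Of the present study, the same section says: "The study is a single arm design with all subjects treated with AeroForm expanders".

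Section 4.1 defines one primary measure, successful expansion with exchange to a permanent implant. It gives a rule for failures and an exception for events unrelated to the device, and adds: "The primary endpoint will be analyzed per breast". The five safety measures come under the heading "4.2 Secondary Outcome Measures". On size, Section 6 says: "Up to 60 subjects will be enrolled in the study".

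**The concern.** A plan built around a randomised comparison cannot be applied whole to one arm, and Section 5.1 does not say which parts survive. Three details add to the doubt:

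- The word *controlled* suggests a comparator that does not exist.
- Section 5.1 can be read as naming a primary safety endpoint, whereas Section 4 lists safety only as secondary.
- The primary outcome is counted per breast, and many women will contribute two. If the two outcomes are correlated, an interval that treats breasts as independent is too narrow.

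At stake would be two analysts working from the same protocol and reporting different endpoint hierarchies, or intervals of different width around the same proportion.

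**Working it through.** **What the protocol settles without the other plan**

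- *Arms.* The synopsis and Sections 1.1 and 3 all describe one arm, and only Section 5.1 adds *controlled*. With no second arm, between-arm comparisons cannot be run, so no analyst has to choose whether to run them.
- *Outcome, unit and failures.* Section 4.1 gives all three, so the per-breast proportion can be computed.
- *Analysis sets.* Section 5.1 names per protocol for the main assessment, with modified intention-to-treat and safety sets besides.
- *Safety wording.* Section 4.1 introduces its measure as the evaluation of performance, and Section 4.2 introduces its list as the evaluation of safety. The natural reading of Section 5.1 is the primary performance endpoint together with those safety endpoints. No section names a primary safety endpoint.

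**How much pairing could matter**

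The protocol states no sample-size, power or interval figure. The one relevant stated number is the 71% bilateral rate of the randomised trial (Section 1.4). It reproduces from the counts there: 168 + 89 = 257 expanders in 150 subjects, and (257 − 150)/150 = 71.3%.

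Assumptions not in the documents: a 95% interval is reported, all 60 subjects enrol, the 71% rate holds here, success is 90% or 95%, and the within-woman correlation ρ lies between 0 and 1.

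1. Bilateral subjects: 60 × 0.71 = 42.6, taken as 43. Breasts: 60 + 43 = 103.
2. Design effect = 1 + (2 × 43/103)ρ = 1 + 0.835ρ.
3. Half-width = 1.96 × √(p(1 − p) × design effect/103).

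| ρ | Width relative to independence | Half-width at 95% success (points) | Half-width at 90% success (points) |
|---|---|---|---|
| 0 | 1.000 | 4.21 | 5.79 |
| 0.1 | 1.041 | 4.38 | 6.03 |
| 0.25 | 1.099 | 4.63 | 6.37 |
| 0.5 | 1.191 | 5.01 | 6.90 |
| 1 | 1.355 | 5.70 | 7.85 |

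A nominal 95% interval that ignored pairing would cover about 93% at ρ = 0.2, 90% at ρ = 0.5 and 85% at ρ = 1.

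The bilateral rate has little influence. If no replacements are counted among the expanders in Section 1.4, ASPIRE gives 34/21 − 1 = 62% and PACE II gives 61/33 − 1 = 85%. For 60 subjects these mean 97 and 111 breasts, with coefficients 74/97 = 0.763 and 102/111 = 0.919. The widening is then 9% to 11% at ρ = 0.25 and 18% to 21% at ρ = 0.5.

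These half-widths are normal approximations. At 95% success and ρ = 0.5 the upper limit is 95 + 5.01 = 100.01%, so the figures show scale only and are not intervals anyone should report.

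**The case for a change.** The strongest case for a change is that it would cost a few sentences in Section 5.1, with no effect on data collection or sample size, and would remove every ambiguity above. Nor can pairing be dismissed. ρ is unknown. Each expander has its own bonded controller (Section 12.7) and most failures in Table 5 belong to a single device, which points to a low ρ. But Table 5 also lists altitude change and operator error, which both sides of one woman could share, and Section 4.1 counts removals for device-related adverse events as failures too.

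Part of this stands. The protocol text does not state a method for pairs, and *controlled* is wrong. The rest does not carry the case. The deferral is to a specific version of a plan that is not among the documents, so silence here does not show an omission there. That plan's trial had the same bilateral structure and had to deal with the same question. Equally, these documents cannot show that it did so.

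Writing in a clustered method now would also be less simple than it looks. Section 1.4 reports that all 7 PACE I and all 33 PACE II subjects completed expansion and reconstruction. If no breast fails here, an intercept-only logistic GEE has no finite estimate and ρ cannot be estimated from the data.

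**Conclusion.** No change to the plan is needed. The missing detail is of a kind that analysts fill sensibly: the comparative parts of the referenced plan lapse in one arm, and the safety phrase points to the measures in Section 4.2. *Controlled* is a clerical slip, contradicted by every other description of the design. Following the text as written gives no demonstrably wrong result.

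The pairing question bears only on the precision of a descriptive proportion, in a study whose stated objective is continued access and whose 60 subjects are a ceiling. With about 103 breasts, the interval would widen by 4% to 10% at ρ = 0.1 to 0.25, which is 0.17 to 0.42 points of half-width at 95% success and 0.24 to 0.58 points at 90%. The extreme, ρ = 1, is 35%. All of this depends on an interval the protocol does not promise, on a naive calculation of it, on full enrolment, on the earlier trial's bilateral rate, and on success rates and a correlation that the documents do not give. The judgement would be different if a performance goal or a test rested on that interval, but none does.
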